9.5 Surgery

Surgery to occur at 4-8 weeks (days 29-56) or subject will be removed from trial unless approved by PI. If pembrolizumab dose 2 is delayed, then there should be at least 2 days between pembrolizumab infusion and surgery.

The ability to perform surgery will be assessed by the surgeon and will be based on physical exam and radiological evaluation. Surgical therapy will be individualized based on the surgical judgment and patient preference and is not dictated by study protocol. Excess tumor tissue samples will also be collected at time of surgical resection after determination that adequate tumor has been taken by surgical pathology for all standard clinical studies. Specific instructions for processing and shipping are provided in Appendices G & H.

9.6 Post-surgery Follow-Up Visit (2-6 weeks following surgery)

Subjects with bulky residual adenopathy such that resection was not attempted will be removed from protocol therapy and should receive standard oncology care as deemed appropriate by the treating physician.

Subjects with positive surgical margins or N2 disease will be removed from protocol and considered for standard of care post-operative radiation +/- standard chemotherapy as deemed appropriate by their physician. Subjects who are completely resected or who refuse or cannot receive adjuvant chemotherapy will be given the option of receiving adjuvant Pembrolizumab.

- Vital signs (temp, B/P, pulse)
- Weight
- ECOG performance status
- Physical exam
- Routine blood work
- Adverse events assessment*
- **Research blood sample (3rd collection).** Research blood: blood will be collected to assess longitudinal analyses of T cell and MDSC phenotypes and blood based biomarkers. 4 tubes of 8.5-ml each will be collected. The tubes used will be ACD anti-coagulated Vacutainer (yellow tops). Samples will be collected and transported/shipped to the Substrate Services Core lab for processing. This blood sample to be collected 2-6 weeks after surgery and prior to adjuvant therapy (Refer to Appendices F and G).

*All AEs that occur prior to the Safety Follow-Up Visit should be recorded. Subjects with an AE of grade > 1 will be followed until the resolution of the AE to grade 0-1 or until the beginning of a new anti-neoplastic therapy, whichever occurs first. SAEs that occur within 90 days of the end of treatment or before initiation of a new anti-cancer treatment should also be followed and recorded.

9.7 Post-Surgery Therapy (Adjuvant Standard Chemotherapy +/- Radiation Therapy)

After surgery, patients should be offered all standard therapies including adjuvant chemotherapy and radiation based on the final pathologic stage of the cancer, tumor margins, and other standard clinical criteria. Patients should receive all standard oncology care as deemed appropriate by the treating physician. Since none of the post-surgical therapy is study specific, post-surgical therapy can be given through the primary oncology team.

9.8 Adjuvant Pembrolizumab

Following completion of all standard adjuvant therapy, including chemotherapy and/or radiation therapy, patients will receive 4 cycles of pembrolizumab 200 mg every 21 days. Patients who receive both adjuvant CT plus adjuvant RT should start Pembrolizumab within 8 months of surgery. Patients who receive only one modality of adjuvant therapy (e.g. CT alone or RT alone) should start Pembrolizumab within 6 months of surgery. Patients who do not receive any adjuvant therapy should start Pembrolizumab within 4 months of surgery

9.8.1 Cycle 1 (Day 1)

- Weight (BSA calculation)
- Vital signs (temp, B/P, pulse)

- ECOG Performance status
- Physical exam
- Adverse events assessment
- Routine blood work
- Thyroid functions (T3, FT4, & TSH)
- Pregnancy test ≤ 3 days (72 hrs.) prior to first dose of pembrolizumab for WOCBP only (per institutional guidelines)
- Pembrolizumab 200 mg IV

9.8.2 Cycle 2 (Day 22)

- Weight (BSA calculation)
- Vital signs (temp, B/P, pulse)
- ECOG Performance status
- Physical exam
- Adverse events assessment
- Routine blood work
- Pregnancy test ≤ 3 days (72 hrs.) prior to first dose of pembrolizumab for WOCBP only (per institutional guidelines)
- Pembrolizumab 200 mg IV

9.8.3 Cycle 3 (Day 43)

- Weight (BSA calculation)
- Vital signs (temp, B/P, pulse)
- ECOG Performance status
- Physical exam
- Adverse events assessment
- Routine blood work
- Pregnancy test ≤ 3 days (72 hrs.) prior to first dose of pembrolizumab for WOCBP only (per institutional guidelines)
- Thyroid functions (T3, FT4, & TSH)
- Pembrolizumab 200 mg IV

9.8.4 Cycle 4 (Day 64)

- Weight (BSA calculation)
- Vital signs (temp, B/P, pulse)
- ECOG Performance status
- Physical exam
- Adverse events assessment
- Routine blood work

- Pregnancy test \leq 3 days (72 hrs.) prior to first dose of pembrolizumab for WOCBP only (per institutional guidelines)
- Pembrolizumab 200 mg IV
-

9.8.5 End of Study Visit (*Safety Follow-up)

End of study evaluation is to occur approximately 30 days or more after last adjuvant Pembrolizumab treatment.

- Vital signs (temp, B/P, pulse)
- Weight
- Performance status
- Physical exam
- Routine blood work
- Thyroid functions (T3, FT4, & TSH)
- Adverse events assessment
- Chest CT if applicable (per radiologic evaluation appendix A)
- Research blood (4th Collection): blood will be collected to assess longitudinal analyses of T cell and MDSC phenotypes and blood based biomarkers. 4 tubes of 8.5-ml each will be collected. The tubes used will be ACD anti-coagulated Vacutainer (yellow tops). Samples will be collected, and transported/shipped to the Substrate Services Core lab for processing (Refer to Appendices F & G).

*All AEs that occur prior to the Safety Follow-Up Visit should be recorded. Subjects with an AE of Grade $>$ 1 related to Pembrolizumab will be followed until the resolution of the AE to Grade 0-1, or investigator deems stable, or until the beginning of a new anti-neoplastic therapy, whichever occurs first. SAEs that occur within 90 days of the end of treatment or before initiation of a new anti-cancer treatment should also be followed and recorded.

9.8.6 Follow-up

Patients should have follow-up as per standard care of the treating institution. Outcome data (recurrence and survival) will be collected every 3-4 months for 2 years after surgery. Following that, collect follow-up every 6 months for up to five years. Follow-up can occur by primary oncology provider and data can be collected by phone.

Every effort should be made to collect information regarding disease status during this follow-up which may include the start of new anti-neoplastic therapy, disease progression, death, end of the study.

10.0 Sample Procurement and Handling

10.1 Blood Specimens

Blood will be collected 4 times to assess longitudinal analyses of T cell and MDSC phenotypes and other blood based biomarkers.

Samples will be collected to detect activated CD8+ T cells with specificity against tumor antigens and CD4 and CD8 functional memory. At each blood collection, 4 tubes of 8.5-ml each will be collected. The tubes used will be ACD anti-coagulated Vacutainer (yellow tops). The following time points will have blood collections

(Outside Sites see appendix G for processing/shipping):

Collection 1: Baseline prior to treatment initiation

Collection 2: After dose # 2 pembrolizumab and prior to surgery

Collection 3: Two to six weeks after surgery prior to initiation of adjuvant chemotherapy.

Collection 4: Three to six weeks after last dose of adjuvant pembrolizumab

**** Note: it is imperative tube is filled to the fill line for proper additive to blood ratio. Specimen is not evaluable if not filled to the fill line. If unable to obtain the 4 required tubes, fill as many tubes as possible to the fill line.

*****If EOS (End of Study) occurs and no adjuvant treatment with Pembrolizumab has occurred, draw Collection #4 at End of Study visit.

10.2 Surgical Specimens

Patients at Duke will be approached to participate in the “DUHS Biospecimen Repository and Processing Core (BRPC)” eIRB 35974 protocol prior to surgery to help coordinate and facilitate tissue acquisition. Tissue will be collected and released as described in this protocol to ensure proper involvement of pathology to minimize the chance that a tissue collection event interferes with appropriate clinical tissue processing and diagnosis. For those subjects that decline participation in this biorepository protocol, tissue will be processed as outlined below.

Tumor specimen samples will be collected at time of definitive surgical resection of tumor. Lung tissue is harvested in the frozen section or gross dissection area of the surgical pathology suite. The tissue is first examined by a certified anatomic pathologist or surrogate (resident, pathology assistant). Relevant margins are inked, removed and examined by frozen section analysis, if necessary. It is imperative that harvesting tissue for use in research trials does not impede accurate initial assessment of critical features of the tumor resection, most notably margin status. After the specimen has been processed for margin status, the frozen section assessment of the specimen is complete (appendix H), a specimen of excess tumor will be released and acquired by the Tumor Immunology correlative science staff for isolation of tumor infiltrating lymphocytes for purposes of this protocol.

OUTSIDE SITES: Please refer to Appendix I for processing/shipping surgical specimen to Duke to the Tumor Immunology Laboratory for TILs analysis. Note that the ability to obtain high quality TILs from **fresh tissue** is highly dependent on the tissue procurement. Delays in tissue processing usually lead to cell death and RNA degradation. Please carefully observe the precautions/instructions pertaining to shipping.

10.2.1 Genomic Analysis (Slides/Blocks)

Response of tumors to immune therapy is in part related to the expression of novel antigens (neoantigens), abnormal patterns of wild type proteins, and/or viral antigens on the tumors cell surface. Genomic studies of the tumor (optional for the subject) will be of interest for comparison to tumor response, immune related side effects, and functional immune biomarkers. Future studies will utilize FFPE from the tumor resected as part of standard of care to perform relevant genomic analysis on the tumor cells. Future scientific studies would be submitted for scientific and IRB review.

10.2.2 Other Biomarkers (blocks)

To ascertain the impact of PD-L1 status on response and endpoints, PD-L1 analysis will be performed by QUALTEK Molecular Laboratories. Duke and sites will ship formalin-fixed paraffin embedded blocks directly to QUALTEK Molecular Laboratories (Newtown, PA) for analysis of PD-L1. Details about shipment are contained in the QualtekMISP Sample Handling Manual.

11.0 TREATMENT

Merck will provide pembrolizumab at no cost for this study. The investigational product is defined as a pharmaceutical form of an active ingredient being tested as a reference in the study, whether blinded or un-blinded. In this study, the investigational product is pembrolizumab. Other medications used in the study as support or escape medication for preventative, diagnostic, or therapeutic reasons, as components of the standard of care for a given diagnosis, are considered non-investigational products.

11.1 Treatments Administered

Patients will receive pembrolizumab as follows:**

Neoadjuvant Pembrolizumab: Cycle 1 day 1: pembrolizumab 200 mg IV

Cycle 2 day 1 (21 days after cycle 1 day 1): pembrolizumab 200 mg IV

Pembrolizumab will be administered as a 30-minute IV infusion (treatment cycle may be delayed up to 3 weeks due to toxicity). Sites should make every effort to target infusion timing to be as close to 30 minutes as possible. However, given the variability of infusion pumps from site to site, a window of -5minutes and +10 minutes is permitted (i.e., allowed infusion time is between 25 and 40 minutes).

Surgery: Standard surgical evaluation to occur after the last dose of pembrolizumab followed by surgical therapy.

Adjuvant chemotherapy: Is a standard consideration as per NCCN guidelines. Patients will be evaluated and offered adjuvant chemotherapy based on standard criteria such as T > 3 cm and/or metastases in N1 and/or N2 lymph nodes. Adjuvant chemotherapy is not study specific and should be given by commercial supply and standard of care.

Adjuvant radiation: Is sometimes a standard consideration as per NCCN guidelines. Patients will be evaluated and offered radiation based on standard criteria such as positive post-operative tumor margin and/or presence of metastases in N2 lymph nodes. Adjuvant radiation is not specific to this study and should be given as per standard of care.

Adjuvant Pembrolizumab: Three to 6 weeks after completion of all standard therapy including adjuvant chemotherapy and/or radiation therapy, patients will receive pembrolizumab 200 mg IV every 21 days for 4 doses.

11.2 Materials and Supplies

Qualified personnel who are familiar with procedures that minimize undue exposure to themselves and to the environment will undertake the preparation, handling and safe disposal of chemotherapeutic agents in a self-contained, protective environment. Unused portions of injectable chemotherapeutic agents that do not contain a bacteriostatic agent or are prepared with unpreserved diluents (i.e., Sterile Water of Injection USP or 0.9% Sodium Chloride for Injection) should be discarded within eight hours of vial entry to minimize the risk of bacterial contamination.

11.2.1 Pembrolizumab

Pembrolizumab will be intravenously administered only at the investigational site. As a result, patient compliance is ensured.

11.3 Dose Selection/Modification

11.3.1 Dose Selection

The rationale for selection of doses to be used in this trial is provided in Section 2 – Background and Rationale.

Details on preparation and administration of pembrolizumab (MK-3475) are provided in the Pharmacy Manual.

11.3.2 Selection and Timing of Doses

Patients in this study will receive neoadjuvant pembrolizumab on Days 1 and 22, and adjuvant pembrolizumab every 21 days for 4 cycles after completion of all standard therapy.

Trial treatment should be administered on Day 1 of each cycle after all procedures/assessments have been completed as detailed on the Trial Flow Chart (Appendix A). Trial treatment may be administered up to 3 days before or after the scheduled Day 1 of each cycle due to administrative reasons.

All trial treatments will be administered on an outpatient basis. Pembrolizumab 200 mg will be administered as a 30-minute IV infusion every 3 weeks. Sites should make every effort to target infusion timing to be as close to 30 minutes as possible. However, given the variability of infusion pumps from site to site, a window of -5 minutes and +10 minutes is permitted (i.e., infusion time is 30 minutes: -5 min/+10 min).

The Pharmacy Manual contains specific instructions for the preparation of the pembrolizumab infusion fluid and administration of infusion solution.

11.4 Pembrolizumab Dose Modifications

Adverse events (both non-serious and serious) associated with pembrolizumab exposure may represent an immunologic etiology. These adverse events may occur shortly after the first dose or several months after the last dose of treatment. Pembrolizumab must be withheld for drug-related toxicities and severe or life-threatening AEs as per Table 1 below.

If pembrolizumab is delayed more than two weeks due to a related AE, then pembrolizumab will be discontinued and patients should proceed to surgical resection when clinically appropriate.

Table 1
Dose Modification Guidelines for Drug-Related Adverse Events

Toxicity	Hold Treatment For Grade	Timing for Restarting Treatment	Treatment Discontinuation
Diarrhea/Colitis	2-3	Toxicity resolves to Grade 0-1.	Toxicity does not resolve within 12 weeks of last dose or inability to reduce corticosteroid to 10 mg or less of prednisone or equivalent per day within 12 weeks.
	4	Permanently discontinue	Permanently discontinue
AST, ALT, or Increased Bilirubin	2	Toxicity resolves to Grade 0-1	Toxicity does not resolve within 12 weeks of last dose.
	3-4	Permanently discontinue (see exception below)	Permanently discontinue
Type 1 diabetes mellitus (if new onset) or Hyperglycemia	T1DM or 3-4	Hold pembrolizumab for new onset Type 1 diabetes mellitus or Grade 3-4 hyperglycemia associated with evidence of beta cell failure.	Resume pembrolizumab when patients are clinically and metabolically stable.
Hypophysitis	2-4	Toxicity resolves to Grade 0-1 Therapy with Pembrolizumab can be continued while endocrine replacement therapy is instituted	Toxicity does not resolve within 12 weeks of last dose or inability to reduce corticosteroid to 10 mg or less of prednisone or equivalent per day within 12 weeks.
	4		
Hyperthyroidism	3	Toxicity resolves to Grade 0-1	Toxicity does not resolve within 12 weeks of last dose or inability to reduce corticosteroid to 10 mg or less of prednisone or equivalent per day within 12 weeks.
	4	Permanently discontinue	Permanently discontinue
Hypothyroidism	2-4	Therapy with pembrolizumab can be continued while thyroid	Therapy with pembrolizumab can be continued while thyroid

Toxicity	Hold Treatment For Grade	Timing for Restarting Treatment	Treatment Discontinuation
		replacement therapy is instituted	replacement therapy is instituted.
Infusion Reaction	3-4	Permanently discontinue	Permanently discontinue
Pneumonitis	2	Toxicity resolves to Grade 0-1	Toxicity does not resolve within 12 weeks of last dose or inability to reduce corticosteroid to 10 mg or less of prednisone or equivalent per day within 12 weeks.
	3-4	Permanently discontinue	Permanently discontinue
Renal Failure or Nephritis	2	Toxicity resolves to Grade 0-1	Toxicity does not resolve within 12 weeks of last dose or inability to reduce corticosteroid to 10 mg or less of prednisone or equivalent per day within 12 weeks.
	3-4	Permanently discontinue	Permanently discontinue
Myocarditis	1-2	Withhold	Give corticosteroids based on AE severity (pred 1-2mg/kg then taper)
	3-4	Permanently discontinue	
All Other Drug-Related Toxicity ^c	3 or Severe	Toxicity resolves to Grade 0-1	Toxicity does not resolve within 12 weeks of last dose or inability to reduce corticosteroid to 10 mg or less of prednisone or equivalent per day within 12 weeks.
	4	Permanently discontinue	Permanently discontinue

Note: Permanently discontinue for any severe or Grade 3 drug-related AE that recurs or any life-threatening event.

^aFor patients with liver metastasis who begin treatment with Grade 2 AST or ALT, if AST or ALT increases by greater than or equal to 50% relative to baseline and lasts for at least 1 week then patients should be discontinued.

^b If symptoms resolve within one hour of stopping drug infusion, the infusion may be restarted at 50% of the original infusion rate (e.g., from 100 mL/hr to 50 mL/hr). Otherwise dosing will be held until symptoms resolve and the subject should be premedicated for the next scheduled dose; Refer to – Infusion Treatment Guidelines for further management details.

^cPatients with intolerable or persistent Grade 2 drug-related AE may hold study medication at physician discretion. Permanently discontinue study drug for persistent Grade 2 adverse reactions for which

Toxicity	Hold Treatment For Grade	Timing for Restarting Treatment	Treatment Discontinuation
treatment with study drug has been held, that do not recover to Grade 0-1 within 12 weeks of the last dose.			

Dosing interruptions are permitted in the case of medical/surgical events or logistical reasons not related to study therapy (e.g., elective surgery, unrelated medical events, patient vacation, and/or holidays). Subjects should resume study therapy within 3 weeks of the scheduled interruption, unless otherwise discussed with the Sponsor. The reason for interruption should be documented in the patient's study record.

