20.8 Evaluating Adverse Events

An investigator who is a qualified physician will evaluate all adverse events according to the NCI Common Terminology for Adverse Events (CTCAE), version 4.0. Any adverse event which changes CTCAE grade over the course of a given episode will have each change of grade recorded on the adverse event case report forms/worksheets.

All adverse events regardless of CTCAE grade must also be evaluated for seriousness.

Table 6 EVALUATING ADVERSE EVENTS: An investigator who is a qualified physician will evaluate all adverse events as to:

V4.0 CTCAE Grading	Grade 1	Mild; asymptomatic or mild symptoms; clinical or diagnostic observations only; intervention not indicated.
	Grade 2	Moderate; minimal, local or noninvasive intervention indicated; limiting age-appropriate instrumental ADL.
	Grade 3	Severe or medically significant but not immediately life-threatening; hospitalization or prolongation of hospitalization indicated; disabling; limiting self-care ADL.
	Grade 4	Life threatening consequences; urgent intervention indicated.
	Grade 5	Death related to AE
Seriousness	A serious adverse event is any adverse event occurring at any dose or during any use of Merck product that:	
	† Results in death ; or	
	† Is life threatening ; or places the subject, in the view of the investigator, at immediate risk of death from the event as it occurred (Note: This does not include an adverse event that, had it occurred in a more severe form, might have caused death.); or	
	† Results in a persistent or significant disability/incapacity (substantial disruption of one's ability to conduct normal life functions); or	
	† Results in or prolongs an existing inpatient hospitalization (hospitalization is defined as an inpatient admission, regardless of length of stay, even if the hospitalization is a precautionary measure for continued observation. (Note: Hospitalization [for an elective procedure] to treat a pre-existing condition that has not worsened is not a serious adverse event. A pre-existing condition is a clinical condition that is diagnosed prior to the use of a Merck product and is documented in the patient's medical history); or	
	† Is a congenital anomaly/birth defect (in offspring of subject taking the product regardless of time to diagnosis); or	

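### Table 1 and its Note give inconsistent pembrolizumab instructions for three endocrine toxicities, so sites could dose similar patients differently

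*Combined protocol and SAP*

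**What the plan says.** Section 11.4 of the protocol gives Table 1 binding force: "Pembrolizumab must be withheld for drug-related toxicities and severe or life-threatening AEs as per Table 1 below". The table has one column for the grades at which treatment is held, one for when it may restart, and one for when it is discontinued.

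The rows and rules that matter here are these:

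- **Hypothyroidism.** The row begins "Hypothyroidism 2-4 Therapy with pembrolizumab can be continued while thyroid". Grades 2-4 stand in the hold column, and the discontinuation cell repeats the permission to continue.
- **Hypophysitis.** Grades 2-4 stand in the hold column, and the restart cell reads "Toxicity resolves to Grade 0-1 Therapy with Pembrolizumab can be continued while endocrine replacement therapy is instituted".
- **T1DM or hyperglycemia.** The restart cell says "Hold pembrolizumab for new onset Type 1 diabetes mellitus or Grade 3-4 hyperglycemia associated with evidence of beta cell failure". The discontinuation cell says "Resume pembrolizumab when patients are clinically and metabolically stable".
- **Hyperthyroidism.** Grade 3 is held until it resolves to Grade 0-1. Grade 4 is permanently discontinued.
- **Note under the table.** "Permanently discontinue for any severe or Grade 3 drug-related AE that recurs or any life-threatening event". It names no endocrine exception.
- **Grade 4.** Table 6 in Section 20.8 defines it as "Life threatening consequences; urgent intervention indicated".

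**The concern.** A dose-modification table that sites must follow should give one action for each toxicity and grade. Here a site that reads the hypothyroidism row by its column heading withholds the drug, while a site that reads the action cells goes on dosing. At Grade 4 the Note adds a third answer, permanent discontinuation, for three endocrine toxicities whose own rows allow treatment to go on or resume.

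The trial is multi-institution (Section 3.2), so each site applies the table itself. The rules govern the second neoadjuvant dose and the four adjuvant doses. The choice between holding and continuing also has a further consequence: the sentence above Table 1 ends pembrolizumab once a related adverse event has delayed it by more than two weeks. One reading can therefore lead to the end of treatment where the other keeps the patient on schedule. What is at stake is patient safety and consistent dosing across sites.

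**Working it through.** No formula applies. The check is a count of rows and a side-by-side reading.

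**Step 1. Count the rows.** Table 1 lists 11 toxicities: diarrhea/colitis; AST, ALT or bilirubin; T1DM or hyperglycemia; hypophysitis; hyperthyroidism; hypothyroidism; infusion reaction; pneumonitis; renal failure or nephritis; myocarditis; and all other drug-related toxicity.

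**Step 2. Sort them by what they say at Grade 4.** Eight direct permanent discontinuation, in line with the Note: colitis, hepatic, hyperthyroidism, infusion reaction, pneumonitis, renal, myocarditis and all other. The remaining 11 - 8 = 3 (T1DM or hyperglycemia, hypophysitis, hypothyroidism) include Grade 4 and allow resuming or continuing.

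**Step 3. Read the endocrine rows grade by grade.** The Note's other limb concerns recurrence of severe or Grade 3 events, so for Grades 2-3 the table below considers a first event.

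| Toxicity and grade | In hold column | Restart cell | Discontinuation cell | Note | Result |
|---|---|---|---|---|---|
| Hypothyroidism 2-3 | yes | continue | continue | not triggered | heading against both action cells |
| Hypothyroidism 4 | yes | continue | continue | discontinue permanently | three different instructions |
| Hypophysitis 2-3 | yes | wait for Grade 0-1; may also continue | 12-week resolution or steroid limit | not triggered | ambiguous: sequence or alternatives |
| Hypophysitis 4 | yes | as above | as above | discontinue permanently | row against Note |
| Hyperglycemia 3 | yes | hold | resume when stable | not triggered | a sequence, with the resume text in the wrong column |
| Hyperglycemia 4 | yes | hold | resume when stable | discontinue permanently | row against Note |
| Hyperthyroidism 3 | yes | at Grade 0-1 | 12-week resolution or steroid limit | not triggered | consistent |
| Hyperthyroidism 4 | yes | discontinue permanently | discontinue permanently | discontinue permanently | consistent |

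New-onset T1DM is listed without a grade. It meets the Note only if the event is life threatening.

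**Step 4. Look for a rule that settles it.** Section 11.5.1 covers corticosteroids, beta-blockers, hormone replacement and insulin for these events, but does not say whether to hold or continue pembrolizumab. Table 6 requires advance sponsor approval before re-exposure after a serious event that the drug may have caused. That is a partial safeguard, but it points back to the protocol's dose-modification guidelines, and so to Table 1. A general exemption of endocrine events from the Note cannot be inferred either, because hyperthyroidism is endocrine and is permanently discontinued at Grade 4.

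**Step 5. Check the analyses.** Section 27.1 defines evaluable patients for the primary endpoint by eligibility and at least one dose of pembrolizumab, so the conflict does not change who is counted. The planned safety summary tabulates treatment-related adverse events by type and grade. The analysis plan lists no exposure or discontinuation-count analysis.

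**The case against.** The strongest reply is that most of this is loose layout. Table 1 does not use its columns strictly: the myocarditis row puts its withholding instruction under restart and steroid advice under discontinuation. In the hypothyroidism row both action cells agree in words, and only the heading disagrees. The T1DM row reads naturally as hold, then resume. The hypophysitis cell can be read as hold to Grade 0-1, then continue on replacement, and the empty Grade 4 line after it may be an extraction fault. Section 3.2.1 also refers to endocrinopathy guidelines in the appendices of the Investigator's Brochure, which are not available here and may help sites.

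Much of this stands. The hypophysitis cell is ambiguous rather than plainly contradictory at Grades 2-3, the T1DM row is a sequence below Grade 4, and nothing here rests on the empty line. The reply does not remove the hypothyroidism mismatch in a table that Section 11.4 makes mandatory, or the clash between the Note and three rows at Grade 4. Guidance in another document would not make the protocol's own text consistent.

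Three stronger readings are tempting, and the documents do not support them:

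- **Every endocrine row gives opposite instructions at every grade.** Hyperthyroidism is consistent, and permanent discontinuation enters the conflict only at Grade 4, through the Note.
- **Sites will dose identical patients differently.** The text permits this but does not show that it happens.
- **A number of affected patients can be stated.** The documents give no event rate. A count of all Grade 2 or higher endocrine events would include hyperthyroidism, which has no conflict, and events after the last dose, when no dosing decision remains.

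**Conclusion.** The inconsistency is real and limited. One row, hypothyroidism Grades 2-4, disagrees with its own column heading. Three of 11 rows disagree with the Note at Grade 4. One cell, for hypophysitis, is ambiguous at Grades 2-3. One instruction, to resume after T1DM or hyperglycemia, is in the wrong column and conflicts with the Note only at Grade 4.

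The Grade 4 finding rests on reading the Note's life-threatening event as Grade 4 in Table 6. Table 6 also has a separate seriousness criterion that depends on the investigator's view of immediate risk of death. If the Note means only that, fewer Grade 4 events would be caught, but the Note does not say so.

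A reader might infer that trial results are compromised. The primary-endpoint population is unaffected, and no listed analysis has been shown to change. The point is one of patient safety and uniform dosing, and it warrants a correction because the table is mandatory and the correction is cheap.

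**What to change.** The sponsor should reconcile the hypothyroidism, hypophysitis and T1DM/hyperglycemia rows, their column headings and the Note. After the change, each toxicity and grade should carry one instruction in the column where a site will look for it, and the relation of the Note to these three rows should be explicit. Which instruction applies is for the sponsor's medical lead; this review does not say which is right and proposes none.

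The cost is table wording in a protocol amendment and a memo to sites. No new procedures or patients are needed.
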